### 3. Concise Summary of Project:

#### Study Design:

[figure not shown]
There will be two parts to this project. Part 1 will be a prospective assessment of the urinary effects of Hiprex in women with RUTIs, such as acidity and concentration of formaldehyde, to determine the best oral concentration to inhibit bacterial growth in urine for each enrolled patient. Part 2 will be a long-term assessment of Hiprex on RUTI evolution in women with a longstanding history of RUTIs, with Hiprex taken at a proper dosing (as established in Part 1) and with regular urine checks at subsequent visits up to one year of follow-up.

Part 1: Women between age 50 and 85 presenting to the outpatient UTSW Urology clinic who are currently taking Hiprex (or any methenamine-containing product) or are willing to be started on Hiprex and do not meet exclusion criteria (see below) will be invited to participate in the study. During their first study visit (V1), they will be consented for this long-term prospective study. The documentation of RUTI based on the current definition of 3 documented and treated UTIs in the past year or 2 in the past 6 months will be recorded. A 3 day diary with recordings of urine pH before each meal and before bed will be obtained to document that the patient has consistent low urine pH (<6), a critical condition for methenamine conversion to formaldehyde. Then the patient will be asked to take a tablet of Hiprex 1gm and to provide one subsequent urine samples at 1 hour after the intake of Hiprex. These midstream urine samples will be processed and transferred to our Lab on campus (K2 building) before being sent to our partnering lab at UTD run by [name] for testing, including urine pH testing, and the measurements of methenamine and aldehyde produced in these urine samples.

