#### Part 2:

Patients already on a methenamine drug will be queried on the history of their exposure (duration of intake, effect on RUTI, current urine pHs, etc). Patients will provide a urine sample. If the urine culture is negative, the patient will begin their prescription of Hiprex by manufacturer recommendations (if not already doing so). If the urine culture returns positive, they will be treated with a course of culture-based antibiotics and will begin Hiprex once their urine results confirm a negative culture.

Based on our preliminary data on seven women followed for one year, the levels in urine (ratioed to urinary creatinine to account for urine dilution) remain fairly stable over time.

Therefore, we don't need to follow women on Hiprex as closely as we intended to at the start of this project. Now we suggest that patients return to clinic at 3 months, 6 months, and 12 months after the onset of their Hiprex treatment to provide urine samples. During these follow-up visits, patients will also fill out a standardized, validated questionnaire regarding UTI symptoms. Data concerning common Hiprex side-effects and compliance with self-administration of Hiprex will also be collected. Hiprex will be stopped when clinically indicated based on the onset of such side-effects. Urine acidity and concentration of methenamine and formaldehyde will be analyzed in these urine samples. Hiprex dosage will be increased if concentration of formaldehyde is not above the threshold for bacteriostatic effects.

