##### Secondary outcomes:

- Severity of UTI symptoms based on validated questionnaire, with the expectation of a decrease in UTI symptom severity while on Hiprex.

- Duration of intervals between UTI episodes considering that Hiprex may lessen the frequency of oral antibiotics usage to treat symptomatic UTI episodes.
- Reduction in number of hospital admission and IV antibiotics (PICC line) for urosepsis and/or pyelonephritis compared to the pre-Hiprex situation.
- Frequency and severity of adverse effects related to Hiprex, requiring treatment interruption, dose adjustment, or discontinuation.
- Evaluation of possible gradual increase in bacterial resistance to formaldehyde by testing its concentration in the urine at each visit, urine acidity, and ability to kill established bacterial strains (UTI89, CFT073)

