#### **4. Study Procedures:**

##### Initial visit:

Patients will be consented for the study. Patients will also be advised to return to clinic sooner than scheduled follow-up visits if they start to develop symptoms of a UTI (pain with urination, cloudy or bloody urine, etc.) or experience any side-effects that may be attributed to Hiprex. Patients who have previously been on a methenamine-containing substance will be asked about their medication history, including the length of time on the medication, the dosage and any changes to dosage, and side-effects experienced while taking the medication. Patients will be prescribed Hiprex 1 g PO BID for 3 months with 4 refills (total of 1 year). Urine samples will be obtained from patients prior to their first dose intake. Those will be mid-stream urine sample, with a collection volume around 30 ml.

Those with negative cultures (after 48-72 hours) will begin their first dose of Hiprex. Those with positive cultures will be treated with a course of culture-based antibiotics and will start their first dose of Hiprex when they can produce negative urine cultures. Using a formaldehyde assay, the concentration of formaldehyde in the urine samples with negative cultures of each patient will be measured. A pH meter will be used to determine the acidity of the urine samples.

In the lab of [name], the following studies will be performed on de-identified urine samples:

**Sample preparation:** The urine samples will be frozen at  $-80^{\circ}\text{C}$ . Upon thawing for assay, the urine will be adjusted to pH 8.0 by adding 50 mM HEPES buffer and checked with pH paper in order to prevent methenamine breakdown, which occurs rapidly at  $\text{pH} < 6$ . The sample will be centrifuged to remove particulates and the soluble portion filter sterilized.

**Formaldehyde assay:** A variety of formaldehyde assays are available (summarized in X1). We will use a glutathione-dependent formaldehyde dehydrogenase (FDH)-based assay (X2). The urine sample will be diluted 10- to 1000-fold and placed in a microtiter dish well. The reaction will also contain 50 mM HEPES buffer (pH 8), 0.5 mM reduced glutathione, 0.5 mM NAD, and FDH (the FrmA protein) purified from *Escherichia coli*. The increase in NADH is proportional to the amount of formaldehyde. The mM extinction coefficient for NADH is 6.27. To ensure the linearity of the reaction, a known amount of formaldehyde will be added to this reaction in a separate reaction.

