#### Follow-up:

Patients will be asked to return to clinic for 3 follow-up visits at: 3 months (V1), 6 months (V2), and 12 months (V3) after starting Hiprex. This research visit timing corresponds to standard-of-care clinic visits include those at 3 months, 6 months, and 12 months.

At each of these visits, patients will be asked to withhold their first dose of Hiprex until they arrive to clinic. Urine samples will be collected at baseline, then 1 hours after the dose intake. These samples will be tested according to the same protocol in the lab of [name]. In addition, patients will be administered a UTI Symptom Assessment (UTISA) questionnaire and queried about any UTI symptoms and Hiprex-associated symptoms since their last visit. If the concentration of methenamine/formaldehyde in the urine sample is found to be inadequate for bacteriostatic or bactericidal activity, the dosage might be increased to 1.5 PO BID, and/or diet-adjustment might be considered to decrease urine pH if found to be not sufficiently acidic. For patients unable to reach appropriate low pH urinary levels after the above modifications, they will be removed from the study and will not continue with the longitudinal portion.

Data:

The dataset will be extracted from EPIC and will include demographic data (age, gender, race, height, weight) as well as culture data from prior urinary tract infections, comorbid conditions (i.e. diabetes, renal insufficiency, etc.), hormonal status, methenamine usage history, and urological history (including possible surgical interventions). See Excel document.

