## **10. Potential Risks:**

- a. To the participants who were already taking Hiprex, there are no direct risks because this study would not change their routines.
- b. To the participants who were not initially taking Hiprex, risks include any adverse side effects associated with the medication; however, patients will be monitored very closely after the start on Hiprex therapy.
- c. Tracked information will be used from patient records (EMR in EPIC), and identifiable information will be removed prior to analysis to ensure anonymity. Thus, all possible efforts will be made to protect patient confidentiality. Potential breach of PHI will be minimized with use of encrypted data devices stored in locked and protected areas.

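### For women already on methenamine, the Part 1 one-hour urine does not control the preceding dose, so carry-over could make the level look higher and more adequate than at follow-up visits

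*Combined protocol and SAP*

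**What the plan says.** Section 3 (Study Design) admits both current methenamine users and women willing to start. After consent and a 3-day urine pH diary, the woman is "asked to take a tablet of Hiprex 1gm and to provide one subsequent urine samples at 1 hour after the intake of Hiprex". The text says nothing about her previous dose.

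Section 4 (Follow-up) is more careful at months 3, 6 and 12: "At each of these visits, patients will be asked to withhold their first dose of Hiprex until they arrive to clinic". It continues: "Urine samples will be collected at baseline, then 1 hours after the dose intake".

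Four other places bear on current users:

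- Section 3 (Part 2) has them "queried on the history of their exposure (duration of intake, effect on RUTI, current urine pHs, etc"). Time of last dose is not named.
- Section 4 (Initial visit) states: "Urine samples will be obtained from patients prior to their first dose intake". Its history items are length of use, dosage and changes to it, and side-effects.
- Section 4 (Data) lists "hormonal status, methenamine usage history, and urological history" and refers to a spreadsheet that is not in the documents.
- Section 10 says that for current users "there are no direct risks because this study would not change their routines".

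The level is used in three ways. Study Design has Part 2 run at the dosing that Part 1 establishes, and Section 14 starts the year of monitoring once dosing is confirmed. Section 13 offers current users a check that their urinary dosing is adequate. A secondary outcome on resistance to formaldehyde is assessed "by testing its concentration in the urine at each visit".

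**The concern.** A woman taking 1 g twice daily may come to the Part 1 test with most of a recent dose still in her system. Her one-hour urine then reflects two doses, whereas the same measurement at month 3 reflects one fresh dose plus what remains from the evening before. The Part 1 value would be too high relative to the later ones. That is the unhelpful direction for a test meant to show whether her dosing is adequate. After a missed dose the error runs the other way.

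Two things are at stake: the per-patient dosing check in Part 1, and the first point of the concentration series. A high first value could make later levels seem to fall when only the sampling conditions changed. Women starting the drug have no carry-over, so first values in the two groups would not mean the same thing. If the time of the last dose was not recorded, the error cannot be removed at analysis.

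**Working it through.** The plan gives no figure to reproduce. Its 100 patients are a pilot goal with no calculation, and it states no half-life or absorption rate. The check has a textual part and an illustrative part.

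**Text**

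| Condition | Part 1 test, current users | Months 3, 6, 12 |
|---|---|---|
| Usual dose withheld | not stated | first dose of the day, until arrival |
| Pre-dose urine | unclear | yes |
| One-hour urine | yes | yes |
| Time of last dose | not named | not named |

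The pre-dose entry is unclear because a first dose has no plain meaning for a woman already taking the drug. Even if that sample is taken just before the tablet, it can reveal carry-over but cannot remove it from the one-hour value.

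**Illustration of size**

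All kinetic inputs are assumptions: first-order absorption and elimination, half-life 3, 4, 5 or 6 h, absorption rate ka of 0.7, 1, 1.5 or 2 per hour, and prior 1 g doses every 12 h. Time in the bladder is not modelled.

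Level from one dose at time t, with ke = ln 2 / half-life:

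C(t) = ka/(ka − ke) × (exp(−ke·t) − exp(−ka·t))

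One-hour level when the last usual dose was d hours before the tablet:

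L(d) = C(1) + C(1+d) + C(1+d+12) + C(1+d+24) + …

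The bias ratio is L(d)/L(12), where 12 h stands for a withheld morning dose on a twice-daily regimen.

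Worked case, half-life 4 h and ka = 1: ke = 0.173 and C(1) = 0.572. Carry-over is 0.573 for d = 4 and 0.145 for d = 12. So L(4)/L(12) = (0.572 + 0.573)/(0.572 + 0.145) = 1.145/0.717 = 1.60.

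Range over all 16 combinations:

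| Hours since last dose | Read at 1 h | Averaged over the hour |
|---|---|---|
| 2 | 1.61-2.02 | 1.82-2.56 |
| 4 | 1.40-1.72 | 1.58-2.18 |
| 6 | 1.22-1.46 | 1.34-1.72 |
| 8 | 1.11-1.26 | 1.17-1.39 |
| 10 | 1.04-1.11 | 1.07-1.16 |
| 12 | 1.00 | 1.00 |
| 24 (missed dose) | 0.68-0.93 | 0.56-0.89 |

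The averaged column is shown because urine accumulates between voids. With a wider half-life range of 2-8 h and ka of 1-2, the one-hour ratio for a dose 2-6 h earlier is 1.13-1.90, upward in every case tried.

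The level just before the tablet, relative to its 12 h value, is 1.58-9.80 for a last dose 2-8 h earlier. A pre-dose urine would therefore help to show whether the dose had been withheld.

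**The case against.** The strongest reply is that little hangs on this value. No written rule changes the dose on the Part 1 level. The increase to a higher dose is tied to follow-up samples, where the first dose is withheld. Section 14 specifies no analysis of levels, and the resistance outcome names no first-visit reference. All of this stands, and it sets the limits of the point. A reader might infer that the UTI result is biased or that a needed dose increase is delayed. The documents support neither: the primary outcome counts UTI events, and the dose step does not use this sample.

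A reader might also infer an unplanned extra tablet in clinic at the consent visit. The text does not establish that. The tablet comes after a 3-day diary, and neither day nor place is stated. Section 10 fits the tablet being the scheduled dose, in which case there is no bias. But that section describes risk and gives no instruction.

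Nor do the documents show that the time of last dose goes unrecorded. It may fall under the open-ended history in Part 2 or in the unseen spreadsheet. It is simply not named.

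Follow-up is not an exact standard either, since neither the evening dose nor the appointment is timed. In the same model a 16-18 h gap gives 0.79-0.96 of the 12 h level. That departure is smaller than the effect of a dose 2-6 h earlier, but it is a reason to record dose times at follow-up too.

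Finally, Part 2 reports fairly stable creatinine-adjusted levels in seven women. Their dose timing is not given, and a creatinine ratio corrects for dilution only.

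**Conclusion.** The point holds in a limited form. For current methenamine users the Part 1 test leaves the preceding dose uncontrolled, while the plan's own follow-up procedure withholds the first dose of the day. If the usual dose was taken a few hours before, the one-hour level is biased upward and towards looking adequate.

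The size, about 1.2-2.0 times the 12 h reference for a dose 2-6 h earlier, rests wholly on assumed kinetics and regimen and applies to methenamine. It carries over to formaldehyde only if the two are proportional, which is unproven: Section 2 describes conversion that depends on time and pH. The bias is small by 8-10 h and nil if the tablet is the scheduled dose. The number of women affected cannot be estimated, because neither the count of current users nor their dose times are given.

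The consequence is confined to the Part 1 per-patient dosing check and the first point of the concentration series. Its weight is low to moderate. The change is worth making because it is nearly free and an unrecorded dose time may not be recoverable later.

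**What to change.** For current users, apply the Section 4 follow-up procedure to the Part 1 test, wherever it takes place:

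1. Withhold the usual dose.
2. Take a pre-dose urine. The Initial visit sample can serve if it is taken at that moment.
3. Give the 1 g tablet as the scheduled dose, not in addition to it. An added tablet on a twice-daily 1 g regimen would make 1 + 1 + 1 = 3 g that day instead of 2 g, and would not fit the Section 10 statement.
4. Take the one-hour urine.

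Record the time of the last dose at every sampling visit. For women already tested with a short or unknown interval since the last dose, do not use the Part 1 level as the reference for later visits.

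The cost is one instruction, at most one extra urine cup per current user, and one data field. No new visit is needed.

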#### Part 2:

Patients already on a methenamine drug will be queried on the history of their exposure (duration of intake, effect on RUTI, current urine pHs, etc). Patients will provide a urine sample. If the urine culture is negative, the patient will begin their prescription of Hiprex by manufacturer recommendations (if not already doing so). If the urine culture returns positive, they will be treated with a course of culture-based antibiotics and will begin Hiprex once their urine results confirm a negative culture.

Based on our preliminary data on seven women followed for one year, the levels in urine (ratioed to urinary creatinine to account for urine dilution) remain fairly stable over time.

Therefore, we don't need to follow women on Hiprex as closely as we intended to at the start of this project. Now we suggest that patients return to clinic at 3 months, 6 months, and 12 months after the onset of their Hiprex treatment to provide urine samples. During these follow-up visits, patients will also fill out a standardized, validated questionnaire regarding UTI symptoms. Data concerning common Hiprex side-effects and compliance with self-administration of Hiprex will also be collected. Hiprex will be stopped when clinically indicated based on the onset of such side-effects. Urine acidity and concentration of methenamine and formaldehyde will be analyzed in these urine samples. Hiprex dosage will be increased if concentration of formaldehyde is not above the threshold for bacteriostatic effects.

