Various prophylactic agents against UTIs have been studied, such as estrogen, cranberry juice/tablets, acupuncture, probiotics, and antiseptics, which differ from antibiotics in that they can affect a variety of microorganisms as opposed to just bacteria. Hiprex (methenamine hippurate) is one of the most popular antiseptics prescribed for RUTIs. Hiprex has been around for nearly a century, yet limited information is known on its exact mechanism of action in the urine and there are no strategies in place to target its use to each treated individual. Furthermore, despite several trials against different daily antibiotic prophylaxis, its role in the management of RUTIs has not been solidly established. Methenamine hippurate functions by producing formaldehyde, which inhibits bacterial growth [cit, Validus]. Previous studies have shown a modest decrease in the rate of re-infection in women with RUTIs after beginning Hiprex compared to the rate prior to initiating the medication; however, these studies have failed to produce meaningful results regarding women with RUTIs who do not have a complicated infection involving urinary catheters for example. Hiprex metabolism and excretion in the urine has been studied in the 60's, 70's and 80's. Although it is known that **formaldehyde production is enhanced by an acid environment**, urinary pH has not been routinely tested in patients who take this medication, a regrettable oversight which might affect the efficacy of this compound in vivo.

Therefore, the purpose of this study is to measure the concentration of formaldehyde in the urine of women with RUTIs on Hiprex; and then, assuming its urinary presence is confirmed at the

proper acid urinary pH, evaluate if such a therapy has favorable effects in decreasing the rate of RUTIs over time.

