**Hiprex (methenamine hippurate) is one of the most widely prescribed antiseptics for the prophylaxis of RUTIs**[cit]. Earliest recorded usage of methenamine as a urinary antiseptic was described in 1899. Methenamine is hydrolyzed to ammonia and formaldehyde, which is bacteriostatic or bactericidal depending on its concentration. The rate of this hydrolysis was found to be greater in solutions with lower pHs, achieving formaldehyde concentrations of clinical use at prescription dosage when the pH was less than 6.0. Although the urine pH range varies from 5 to 8, a recent study from our group in post-menopausal women identified an average urine pH around 6.0 with daily variability in several patients, possibly related to diet intake. Furthermore, as methenamine is hydrolyzed, the production of ammonia alkalinizes the solution, slowing down the reaction. Thus, in 1961, in order to increase efficacy, its formulation with adding hippurate, which increases the acidity of urine, as Hiprex, was developed.

**A literature review on the metabolism and urinary excretion of methenamine produced sparse results.** Studies by Gollamudi and Strom detailed the use of silica cartridges to determine the concentration of methenamine and formaldehyde in a solution and test this new method on human urine after administration of Hiprex to subjects. However, this work has limitations, since only 11 participants were tested and the urine samples were only taken after the first dose of Hiprex rather than after several days or months of Hiprex intake. Strom also analyzed the kinetics of methenamine, finding that a methenamine concentration of 750 µg/mL at pH 6.0 could produce bactericidal concentrations of formaldehyde after 3 hr and that the hydrolysis of methenamine occurred 20 times faster at a pH of 5.0 versus 6.0^14. Another study determined that the concentration of formaldehyde in urine adequate to produce a bacteriostatic effect (25 µg/mL) could be attained by adding 0.6 mg/mL of methenamine to urine at a pH ≤ 5.7 or 1 mg/mL at pH ≤ 5.85. Because the two latter experiments produced their results *ex vivo*, the rate of excretion of methenamine into the urine and the proof of its metabolism of conversion to formaldehyde in a patient's urine after an oral intake of 1 gm twice a day as currently recommended remains untested.

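### The Part 2 dose rule acts on urinary formaldehyde alone, although that reading mixes drug delivery, pH, bladder dwell and unrecorded bench time

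*Combined protocol and SAP*

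**What the plan says.** **The rule.** Section 3, Part 2: "Hiprex dosage will be increased if concentration of formaldehyde is not above the threshold for bacteriostatic effects". Methenamine and acidity are to be analysed in the same samples, but the rule does not use them.

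**The follow-up text differs.** Section 4, Follow-up, considers methenamine and formaldehyde together and makes an increase to 1.5 twice daily (unit not printed, read here as grams) discretionary. It adds that "diet-adjustment might be considered to decrease urine pH if found to be not sufficiently acidic" and that "For patients unable to reach appropriate low pH urinary levels after the above modifications, they will be removed from the study".

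**Sampling.** In Part 1 the woman is asked to "take a tablet of Hiprex 1gm and to provide one subsequent urine samples at 1 hour after the intake of Hiprex". At follow-up the morning dose is withheld until arrival: "Urine samples will be collected at baseline, then 1 hours after the dose intake". Neither section says which follow-up sample decides the dose.

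**Handling.** Section 4, Initial visit, freezes samples at -80°C and continues: "Upon thawing for assay, the urine will be adjusted to pH 8.0 by adding 50 mM HEPES buffer". The stated reason is that methenamine breaks down rapidly below pH 6. No limit is set on the time from collection to freezing, and neither that time nor the time of the previous void is to be recorded.

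**Kinetics cited.** Section 2 reports that "a methenamine concentration of 750 µg/mL at pH 6.0 could produce bactericidal concentrations of formaldehyde after 3 hr" and that hydrolysis is 20 times faster at pH 5.0 than at 6.0. It gives 25 µg/mL as the bacteriostatic level, reached with 0.6 mg/mL methenamine at pH 5.7 or below, or 1 mg/mL at pH 5.85 or below, with no time stated. These are ex vivo results.

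**The concern.** Formaldehyde in a urine sample is the product of methenamine delivered, pH, and time at that pH, first in the bladder and then on the bench. The plan measures the first two but neither fixes nor records the third, and the Part 2 rule looks only at the product.

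Two errors are possible. A woman with adequate methenamine and acid urine may read low because conversion is unfinished, and be moved to 50% more drug. The follow-up text does not protect her: if her pH is already below 6, diet adjustment does not apply and more drug is the only listed response. Conversely, a woman whose urine was below threshold when voided may read above it because conversion continued before freezing, and be left unchanged.

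This touches the first stated aim: "the purpose of this study is to measure the concentration of formaldehyde in the urine of women with RUTIs on Hiprex". Part 1 is meant to find each woman's best dose, and sections 3 (Recruitment) and 14 build on properly established dosing when planning a later randomised trial.

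**Working it through.** The 3-hour figure in section 2 cannot be reproduced, because the documents give neither a rate constant nor the bactericidal concentration. What can be checked is how strongly a reading depends on time and pH.

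**Assumptions (not in the documents):** first-order conversion; formaldehyde proportional to methenamine; rate log-linear in pH between 5 and 6, using the 20-fold figure; bladder emptied at the baseline sample.

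**1. Time, at pH 6.0 and equal methenamine.** If a fraction x is converted by 3 hours, then k = -ln(1 - x)/3 and F(1 h)/F(3 h) = [1 - (1 - x)^(1/3)]/x.

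| x | 0.01 | 0.05 | 0.20 | 0.50 |
|---|---|---|---|---|
| ratio | 0.334 | 0.339 | 0.358 | 0.413 |

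If the bladder fills steadily, so that mean dwell is half the hour, the ratio to the same 3-hour batch value is 0.17 to 0.21.

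**2. pH.** The 3-fold time gap equals ln 3/ln 20 = 0.367 pH units, so 1 hour at pH 6.0 - 0.367 = 5.63 matches 3 hours at pH 6.0. Relative to that benchmark, with the bactericidal level varied from 25 to 200 µg/mL, 1 hour gives:

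| pH | 5.85 | 5.7 | 5.5 | 5.0 |
|---|---|---|---|---|
| multiple of pH 6.0 3-hour value | 0.53–0.55 | 0.82–0.84 | 1.4–1.5 | 3.8–6.2 |

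The range where 1 hour falls short is about 5.63 to 6.0. The below-6 criterion admits it, and section 2 reports an average pH around 6.0 in post-menopausal women.

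**3. Bench time.** At low conversion and the same rate on the bench, 1 hour of dwell plus b hours before freezing reads (1 + b)/3 of the 3-hour value: 0.67 at b = 1 and 1.00 at b = 2. Relative to the urine as voided, the reading is inflated (1 + b)-fold, that is 2-fold and 3-fold. The actual bench rate is not in the documents.

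**4. Does it cross the threshold?** Let L be formaldehyde after 3 hours at 750 µg/mL and pH 6.0. The 1-hour reading is below 25 µg/mL if L is below 25/0.334 = 75 (25/0.413 = 61 at the other end of the range). L is not given. The bacteriostatic pair, if it was reached at an unstated time t (hours), scales to:

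- L = 25 × (0.75/0.6) × 20^(-0.3) × 3/t = 38.2/t
- L = 25 × (0.75/1.0) × 20^(-0.15) × 3/t = 35.9/t

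A third of each gives a 1-hour reading of 12.0/t to 12.7/t: about 24 to 25 µg/mL at t = 0.5, 12 to 13 at t = 1, and 8.0 to 8.5 at t = 1.5. The trigger is thus met unless t was under about 0.5 hour, with no bench time or residual drug added.

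**5. Effect of the dose step.** Multiplying by 1.5 takes 12.0–12.7 to 17.9–19.1 µg/mL. Any reading above 25/1.5 = 16.7 would cross 25.

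**The case against.** The strongest case on the other side has five parts.

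- **The benchmark is not the trigger.** The 3 hours refers to a bactericidal level ex vivo; the rule uses the bacteriostatic level, for which no time is given. This stands. A reader might infer that the 1-hour sample generally reads about a third of the level that matters. The documents do not support that: the ratio needs pH 6.0 and equal methenamine, and the plan seeks pH below 6.
- **More drug does help.** A reader might infer that a higher dose cannot correct a low reading. It can in part: formaldehyde rises with methenamine, and readings of 16.7 to 25 µg/mL would cross the threshold at 1.5 times the dose.
- **A 3-hour void would not settle the matter.** With steady filling, mean dwell in such a void is 1.5 hours, so it reads about L/2. At t = 1 that is 18 to 19 µg/mL, still below 25, and 1.5 times the dose gives 27 to 29. In that case the increase might be the right response. Section 2 also advises frequent voiding, so 3 hours is not established as the relevant dwell.
- **The reading may be too high.** Bench conversion, drug left from the evening dose, or use of the pre-dose sample would all raise it. This stands, and it is why the direction is left open.
- **The follow-up text is discretionary.** Section 4 does weigh methenamine and pH. But it conflicts with the mandatory wording of section 3, has no response to insufficient time, and does not name the deciding sample.

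The stability of levels in seven women over a year is no rebuttal, because a consistent timing error would also look stable. The planned test of killing bacterial strains is not linked to dosing.

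**Conclusion.** The point holds in this form: the rule in section 3, Part 2 can give a wrong dose decision, and the reported formaldehyde can be biased, because the reading combines four influences and the rule separates none of them. Near pH 6.0 with equal methenamine, 1-hour formaldehyde is 0.33 to 0.41 of the 3-hour value; by about pH 5.63 the shortfall against the pH 6.0 benchmark has gone; and bench conversion could reverse it. These figures rest on the kinetic assumptions listed, and the unknown L, t and bench rate prevent any statement of net direction.

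A reader might also infer that the trial will systematically over-dose, or that its primary result is compromised. Neither follows. The direction of error is unsettled, and the count of UTI events is not mis-measured. The issue should be fixed, with medium confidence about its practical size.

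**What to change.** 1. **Stop conversion at collection.** Measure pH on the fresh urine, then add the pH 8 buffer to the assay aliquot immediately instead of at thaw. Keep unbuffered urine for culture and the bacterial-killing test. Record the times of the previous void, collection and freezing.
2. **Align section 3, Part 2 with section 4, Follow-up.**
   - Raise the dose only when creatinine-ratioed total methenamine equivalents are low. The acid-treated assay in section 4 already measures the sum of methenamine and formaldehyde, which does not change as methenamine converts.
   - When methenamine is adequate but pH is high, acidify first.
   - Do not escalate on 1-hour formaldehyde alone.
   - State whether the pre-dose or the 1-hour sample decides.

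Report methenamine, formaldehyde and pH together before and after each change. The investigators should set the clinical cut-offs.

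The cost is a little more handling at collection and three recorded times. No new visit, assay or later void is needed.
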